1203 returns a drug, the amount used and unused will be documented, and an explanation for any
1204 inadvertent loss or destruction of supplies will also be recorded.

1205 Ensuring compliance and reconciliation: Site personnel will assess dosing regimen compliance and
1206 drug reconciliation in an ongoing manner. At each subject visit, subject compliance will be evaluated
1207 and documented, including calculating the expected amount of consumed drug given the regimen and
1208 amount of time between visits. This figure will be compared with the amount dispensed minus the
1209 amount the subject returned. Site personnel will question the subject regarding any discrepancies in
1210 these amounts and document the explanation.

1213 Insulin Storage: Insulin will be stored per product labeling as follows:

Insulin	Temperature	Use up to
In use (opened)	Room temperature: up to 86°F	28 days
Not in use (unopened)	Room temperature: up to 86°F	28 days
Not in use (unopened)	Refrigerated: 36°F to 46°F	Expiration date

1214

1215

1216

1217

1218 **10 STATISTICAL CONSIDERATIONS**

1219 The approaches to sample size and statistical analyses are summarized below. A detailed statistical
1220 analysis plan will be written and finalized prior to the completion of the study.

1224 **10.1 Sample Size**

1225 We plan on 132 subjects finishing the study, leading to a potential enrollment of 160, with up to 17.5%
1226 attrition. We base our analysis on our previous decision-support trial [7] which recruited N=120
1227 subjects and concluded with N=96 yielding effect size of 0.2 on key parameters, and on the feasibility
1228 and safety study described in the background. In this study, 11 T1DM pump users tested a prototype of
1229 the DSS leading to an estimated moderate effect size of 0.5 (Cohen D method). Assuming a substantial
1230 reduction of effect size due to (i) the focus on MDI patients, (ii) the presence of CGM in both the
1231 experimental and the control groups, and (iii) the translation of the effect to an uncontrolled
1232 environment similar to the environment of our previous trial [7], we assume a small to medium effect
1233 size. Using the statistical analysis presented below, a 0.15 effect size, with 2 groups randomized in a
1234 ratio of 2:1 (experimental-control), and 3 repeated measures (inter measure correlation of 0.5) leads to
1235 a required sample size of N=132 (expected power of 95.6%) [15].

1236 **10.2 Primary Endpoints Analyses**

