1237 The primary analysis will follow the intention-to-treat principle [16]. It will include all subjects and the
1238 data will be analyzed in the group to which the subjects were assigned through randomization. Percent
1239 in range (70-180 during the day and 80-140 at night) will be computed over each month of data and
1240 entered in a Repeated Measure ANOVA, where the within-between interaction (group x period) will
1241 be studied.

1243 **10.3 Secondary Efficacy Analyses**

1244 In addition to the primary endpoint we will study:

- 1245 • HbA1c: estimated effect size of 0.15; repeated measures ANOVA, 2 groups, 2 measures,
1246 results in power of 90% with current enrollment;
- 1247 • Exposure to hypoglycemia, as measured by the percent of time spent below 70mg/dL and by
1248 the Low BG Index [13]; estimated effect size 0.25; power for repeated measures ANOVA 2x3
1249 >99%;
- 1250 • Exposure to hyperglycemia, as measured by the percent of time spent above 300mg/dL;
1251 estimated effect size 0.2; power for repeated measure ANOVA 2x3 = 99%;
- 1252 • Glucose variability as measured by the Average Daily Risk Range [14] (over 2-week period);
1253 estimated effect size 0.15; power for repeated measure ANOVA 2x6 = 95%.

1255 **10.4 Questionnaires**

1256 The following questionnaires will be completed at the randomization visit:

- 1257 • Diabetes Specific Personality Questionnaire
- 1258 • Clarke Hypoglycemia Awareness Scale [17]
- 1259 • Fear of Hypoglycemia Survey (HFS-II) [18]
- 1260 • Low Blood Sugar Survey
- 1261 • High Blood Sugar Survey
- 1262 • Diabetes Distress Scale
- 1263 • Technology Expectations Survey (CGM+DSS group)

1265
1266 The following questionnaires will be completed at the final visit at week 12:

1267 • Clarke's Hypoglycemia Awareness Scale
1268 • Fear of Hypoglycemia Survey (HFS-II)
1269 • Low Blood Sugar Survey
1270 • High Blood Sugar Survey
1271 • Diabetes Distress Scale
1272 • Technology Acceptance Survey (CGM+DSS group)

1273
1274 For each questionnaire, mean \pm SD values or percentiles appropriate to the distribution will be given
1275 by randomization group for the total score and each subscale. For questionnaires administered to both
1276 randomization groups comparisons will be made using similar ANCOVA models as described above
1277 for the primary endpoints. No formal adjustment will be made for multiple comparisons.

1278
1279 **10.5 Primary Safety Analyses**
1280 All subjects will be included in these analyses.

1281

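### The only primary test named in 10.2 is group x period; unless baseline counts as a period, a steady benefit of any size is detected only at the false-positive rate

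*Combined protocol and SAP*

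**What the plan says.** Section 1.3.7 defines the primary outcome as an increase in percent time in range, and 1.3.1 sets the comparison as CGM+DSS against CGM alone. Section 10.2 computes percent in range per month of data, which is then "entered in a Repeated Measure ANOVA, where the within-between interaction (group x period) will" be studied. It mentions no group main effect, baseline term, averaged contrast or direction.

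Section 10.1 powers this analysis with an effect size of 0.15, a "ratio of 2:1 (experimental-control), and 3 repeated measures (inter measure correlation of 0.5) leads to" N=132 with 95.6% power. No alpha is given.

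The neighbouring sections bear on the role of baseline without settling it:

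- Section 10.3 gives "HbA1c: estimated effect size of 0.15; repeated measures ANOVA, 2 groups, 2 measures". HbA1c is drawn only at screening and week 12, so baseline is a level there.
- For time above 300 mg/dL it gives "estimated effect size 0.2; power for repeated measure ANOVA 2x3 = 99"%, and for the two-week Average Daily Risk Range "estimated effect size 0.15; power for repeated measure ANOVA 2x6 = 95"%. It does not name the effect tested.
- Section 10.4 says that for questionnaires given to both "randomization groups comparisons will be made using similar ANCOVA models as described above" for the primary endpoints. No ANCOVA is described above it.
- Section 4.1 collects two weeks of CGM to characterise baseline control. Section 10.2 gives those data no role.

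The opening of Section 10 says that a detailed "analysis plan will be written and finalized prior to the completion of the study".

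**The concern.** A group x period interaction compares the group difference in one period with the group difference in another. If every period follows randomization, a system that helps equally in all three months gives no interaction, however large the benefit. The test also has no direction: a benefit that wears off can give the same F statistic as one that builds up.

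The trial could therefore be declared negative for a steadily effective system and positive for a waning one. This is the test that decides whether the trial succeeds, and the sample size rests on it.

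**Working it through.** **Inputs.** From 10.1: N=132 at 2:1 (88 and 44), 3 measures (m), correlation rho=0.5, effect size 0.15 read as Cohen f. Assumed: alpha 0.05 and equal correlation between all periods.

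**1. Which test does the stated power belong to?**

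- Interaction: lambda = f²·N·m/(1−rho) = 0.0225 × 132 × 3/0.5 = 17.82, df 2 and 260. Power is 97.2%. Multiplying lambda by 8/9 for 2:1 allocation gives 15.84 and 95.3%. The plan states 95.6%.
- Group main effect: lambda = f²·N·m/(1+(m−1)·rho) = 0.0225 × 132 × 3/2 = 4.455, df 1 and 130. Power is 55%.

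The sizing belongs to the interaction, so the wording of 10.2 is not a slip. For the 2x3 endpoints in 10.3, main-effect power would be 94% (f=0.25) and 80% (f=0.20), below the stated >99% and 99%; the interaction gives >99% for both.

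**2. Is baseline a period?** Three facts point to no:

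- 12 weeks by month gives exactly three measures.
- The run-in lasts two weeks, so it is not a month of data.
- A two-week measure given as 2x6 fills the 12 randomized weeks; with baseline there would be seven periods. Only this count is informative, because the stated 95% matches neither test (interaction 99.9%, main effect 61%).

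**3. Power when all three periods follow randomization.** Let D be the monthly group differences in SD units. Then f² = (2/3)(1/3) × mean of (D − mean D)².

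A constant D gives f=0 and lambda=0, so power equals alpha exactly. In simulation (20,000 runs each), constant benefits of 0.2, 0.3, 0.5 and 0.8 SD were detected in 4.8%, 4.9%, 4.9% and 4.8% of runs.

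For D = (0, 0.5, 0.5), the mean squared deviation is 1/18, f² = 1/81 and lambda = 132 × 3/(81 × 0.5) = 9.78. D = (0.5, 0.5, 0) gives the same value.

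| Monthly benefit (SD) | Interaction power |
|---|---|
| constant, any size | 5% |
| 0.25, 0.5, 0.5 | 27% |
| 0.1, 0.5, 0.5 | 60% |
| 0, 0.5, 0.5 | 80% |
| 0.5, 0.5, 0 | 80% |
| 0.8, 0.4, 0 | 98% |

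**4. The three-month mean difference.** The variance of a subject's three-month mean is (1+2×0.5)/3 = 2/3. The standard error of the difference is √[(2/3)(1/88+1/44)] = 0.151. A constant 0.5 SD gives noncentrality 3.32 and 91% power; 0.3 SD gives 1.99 and 51%.

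Adjusting for a baseline that correlates r with each month reduces the variance to 2/3 − r². With r=0.5 (assumed) it is 0.417, and power is 99% (0.5 SD) and 70% (0.3 SD).

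**5. Power if baseline is a fourth period.** D = (0, 0.5, 0.5, 0.5) gives lambda = 11.0 on 3 and 390 df, power 80%. D = (0, 0.3, 0.3, 0.3) gives lambda = 3.96, power 35%. Both fall below the adjusted mean difference in step 4.

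**The case against.** **The plan never excludes baseline.** Section 10.2 says each month of data, not each month after randomization. HbA1c shows that the authors use the interaction as a change-from-baseline test: with f=0.15, m=2 and the 8/9 factor, lambda is 10.56 and power 89.7%, against the stated 90%. The ANCOVA reference in 10.4 may be a trace of a baseline-adjusted primary model. This stands to the extent that the 5% is conditional. But HbA1c has only two possible time points, so it does not put baseline into 10.2. Three measures that include baseline would leave only two months of a 12-week follow-up. The interaction also loses power under the other reading.

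**A constant effect may not be the expected shape.** The optimization routine in 1.3.1 works from a month of collected data, so some benefit may build after month 1. With 0, 0.5, 0.5 SD, the interaction has 80% power, against about 60% for the unadjusted mean difference and 80% with baseline adjustment (r=0.5, simulated). This stands: the mean difference is not better for every shape. Other modules, such as the bolus calculator and the hypoglycemia alert, act from the start. A test that rewards fading as much as build-up also does not answer the stated question.

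**A detailed SAP is promised.** That gives time to correct the test, but the protocol's primary test and sample size already rest on the interaction.

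**The minimum repair is smaller.** Stating the role of baseline and naming the contrast would remove the ambiguity. Equal monthly weights and baseline adjustment are one reasonable choice, though they match the stated outcome directly.

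**Conclusion.** The concern holds. The only primary test named is the interaction, and the stated power reproduces approximately for it (97.2%, or 95.3% allowing for 2:1, against 95.6%) and not for a group main effect (55%). If baseline is not a period, which is the best-supported reading but is nowhere stated, a steady benefit of any size is detected only at alpha, against 91% (0.5 SD) or 51% (0.3 SD) for the three-month mean difference. If baseline is a fourth period, the figures are 80% and 35%, against 99% and 70% for the baseline-adjusted mean difference.

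These figures assume alpha 0.05, compound symmetry at 0.5 and, where baseline is used as a covariate, a correlation of 0.5 with each month. That a constant effect is detected only at alpha is algebra and holds at any alpha. The point should be corrected before the data are analysed.

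**What to change.** - **10.2:** make the primary test the between-group difference in percent time in range averaged over weeks 0-12 (the equally weighted mean of the three monthly differences), from a longitudinal model adjusted for run-in CGM time in range. Say explicitly that baseline is a covariate and not a level of period. Keep group x period as a supportive check on whether the effect changes over time.
- **10.3:** name the same contrast for the 2x3 and 2x6 CGM endpoints. HbA1c needs no change.
- **10.4:** make the ANCOVA reference match the model in 10.2.
- **10.1:** restate the power for the new contrast and give the alpha.

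The change is to wording and uses data already collected, but the headline power will fall. As an illustration, f=0.15 read as a between-group effect is 0.15/√(2/9) = 0.318 SD. At N=132 that gives about 55% power unadjusted, and 62%, 76% or 87% for an assumed baseline correlation of 0.3, 0.5 or 0.6. The documents give no separate effect size for the mean difference, so the sponsor should supply and justify one when restating the power.

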380 with an A1c <8%;

381 3. Improved psycho-behavioral markers and acceptance of the system feedback by patients,
382 including:

383 a. Improved patient/parent diabetes quality of life scores;

384 b. Improved hypoglycemia perception/awareness and reduced patient/parent fear of
385 hypoglycemia in those with hypoglycemia unawareness and/or history of severe
386 hypoglycemia at the baseline.

387

388 *Main Safety Endpoints:*

- 389 • Episodes of severe hypoglycemia
- 390 • Episodes of diabetic ketoacidosis (DKA)
- 391 • Other serious adverse events

392

393 *Interim Analysis:*

394 All CGM-related study endpoints and data collected will be analyzed for the first 6 weeks of study
395 intervention in the first 40 subjects.

396

397 **1.4 General Considerations**

398 The study is being conducted in compliance with the policies described in the study policies document,
399 with the ethical principles that have their origin in the Declaration of Helsinki, with the protocol
400 described herein, and with the standards of Good Clinical Practice (GCP). (www.wma.net/en/30publications/10policies/b3/)

401 Data will be directly collected in case report forms, which will be considered the source data.

402 There is no restriction on the number of subjects to be enrolled by each site towards the overall
403 recruitment goal.

406 The protocol is considered a significant risk device study, due to the fact that the inControl Advice
407 system is experimental. Therefore, an investigational device exemption (IDE) from the U.S. Food and
408 Drug Administration (FDA) is required to conduct the study.
409

410 This study is supported by third party collaborators for the provision of study drugs, devices, and
411 software. Current study collaborators are:

412 • Novo Nordisk (Bagsværd, Denmark)
413 • TypeZero Technologies Inc., (Charlottesville, VA)

414 **2 SUBJECT SCREENING AND ENROLLMENT**

415

416 **2.1 Study Population**

417 Up to 30 pilot subjects may be enrolled for pilot DSS system testing. These subjects will sign a
418 separate Pilot Subject consent form. Pilot subjects may also participate in the main study.

419

420 Enrollment for the main study will proceed with the goal of at least 132 subjects ≥ 15 years old
421 completing the trial. A maximum of 160 subjects may be enrolled in the study in order to achieve
422 that goal.

423

424 **2.2 Eligibility and Exclusion Criteria**

425 **2.2.1 Eligibility**

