930 **7.1.2 Safety Measures**

931

932 **7.1.2.1 Hypoglycemia Safety Protocol**

933 All subjects will be required to set the CGM hypoglycemia threshold alarm to a value no less than 70
934 mg/dL.

935

936 If a subject receives a CGM hypoglycemia threshold alarm or notes that the CGM glucose is <70
937 mg/dL, confirmatory fingerstick testing will be recommended and the subject will be instructed to treat
938 hypoglycemia with ~16 grams of fast-acting oral glucose.

939

940 **7.1.2.2 Hyperglycemia Safety Protocol**

941 Subjects will be required to set the CGM hyperglycemia threshold alarm to a value no greater than 300
942 mg/dL.

943

944 If a subject receives a CGM hyperglycemia threshold alarm or notes that the CGM glucose is ≥ 300
945 mg/dL, confirmatory fingerstick testing will be recommended.

946

947 If a subject's CGM reading is ≥ 300 mg/dL for over 1 hour, or ≥ 400 mg/dL at any point, the subject
948 will be instructed to take the following steps:

949

950 • Perform a blood ketone measurement with the study ketone meter. Subjects will also be
951 encouraged to check ketones if they are clinically concerned.

952 • Correction insulin may be taken per the subject's usual routine (CGM group) or per the
953 inControl Advice recommendation (CGM+DSS group).

954 • Subjects will be instructed to administer correction insulin per the subject's usual routine
955 (CGM group) or per the inControl Advice recommendation (CGM+DSS group) for ketones
956 ≥ 0.6 mmol/L and to additionally notify study staff for ketones ≥ 3.0 mmol/L.

957

958 **7.1.2.3 Study System Failure**

959 If the inControl Advice APP stops working, subjects will be instructed to resume their regular home
960 insulin therapy until he/she can contact study staff for confirmation of the current carbohydrate
counting parameters or until the study system can be repaired or replaced.

961 **8 ADVERSE EVENTS, DEVICE ISSUES, POTENTIAL RISKS, AND STOPPING RULES**

962 **8.1 Adverse Event Definition**

963 A reportable adverse event for this protocol includes any untoward medical occurrence that meets
964 criteria for a serious adverse event or any unanticipated medical occurrence in a study subject that is
965 study- or device-related, including severe hypoglycemia as defined below and severe
966 hyperglycemia/diabetic ketoacidosis (DKA) as defined below. Skin reactions from sensor placement
967 are only reportable if severe and/or required treatment.

968

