969 Hypoglycemic events are recorded as Adverse Events (severe hypoglycemic event) if the event
970 required assistance of another person due to altered consciousness, and required another person to
971 actively administer carbohydrate, glucagon, or other resuscitative actions. This means that the
972 participant was impaired cognitively to the point that he/she was unable to treat himself/herself, was
973 unable to verbalize his/ her needs, was incoherent, disoriented, and/or combative, or experienced
974 seizure or coma. These episodes may be associated with sufficient neuroglycopenia to induce seizure
975 or coma. If plasma glucose measurements are not available during such an event, neurological
976 recovery attributable to the restoration of plasma glucose to normal is considered sufficient evidence
977 that the event was induced by a low plasma glucose concentration.

978
979 Hyperglycemic events are recorded as Adverse Events (severe hyperglycemic event) if the event
980 involved DKA, as defined by the Diabetes Control and Complications Trial (DCCT) and described
981 below, or in the absence of DKA if evaluation or treatment was obtained at a health care provider
982 facility for an acute event involving hyperglycemia with ketosis.

983
984 Hyperglycemic events are classified as DKA if the following are present:

- 985 • Symptoms such as polyuria, polydipsia, nausea, or vomiting;
- 986 • Serum ketones >1.5 mmol/L or large/moderate urine ketones;
- 987 • Either arterial blood pH <7.30 or venous pH <7.24 or serum bicarbonate <15 ; and
- 988 • Treatment provided in a health care facility

989 **8.2 Recording of Adverse Events**

990 Throughout the course of the study, all efforts will be made to remain alert to possible adverse events
991 or untoward findings. The first concern will be the safety of the study participant, and appropriate
992 medical intervention will be made.

993
994 All reportable adverse events whether volunteered by the subject, discovered by study personnel
995 during questioning, or detected through physical examination, laboratory test, or other means will be
996 reported on an adverse event form online. Each adverse event form is reviewed by the Medical
997 Monitor at the Coordinating Center to verify the coding and the reporting that is required.

998
999 The study investigator will assess the relationship of any adverse event to be related or unrelated by

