1134 CGM. If these reactions occur, different adhesives or “under-taping” (such as with IV 3000,
1135 Tegaderm, etc.) will be tried, sites will be rotated frequently, and a mild topical steroid cream or other
1136 medication may be required.

1137 Whenever the skin is broken there is the possibility of an infection. The CGM sensors are inserted
1138 under the skin. It is possible that any part that is inserted under the skin may cause an infection. These
1139 occur very infrequently, but, if an infection was to occur, oral and/or topical antibiotics can be used.
1140 The risk of skin problems could be greater if you use a sensor for longer than it is supposed to be used.
1141 Therefore, participants will be carefully instructed about proper use of the sensor.

1142 Data downloaded from the CGM and blood glucose and ketone meters will be collected for the study
1143 as measures of diabetes self-management behaviors. Some people may be uncomfortable with the
1144 researchers' having such detailed information about their daily diabetes habits.

1145

1146 **8.6 Study Stopping Criteria**

1147

1148 **8.6.1 Subject Discontinuation of Study Treatment**

1149 Rules for discontinuing inControl Advice (if randomized to CGM+DSS group) or study CGM use (if
1150 randomized to the CGM group) are as follows:

- 1151 1. One episode of severe hypoglycemia, or of hyperglycemia/DKA as defined in Section 8.1
- 1152 2. One serious adverse event related to device malfunction.
- 1153 3. The subject requests that the treatment be stopped
- 1154 4. Subject pregnancy

1155

1156 **8.6.2 Criteria for Suspending/Stopping Overall Study**

1157 In the case of inControl Advice resulting in a severe hypoglycemia or severe hyperglycemia event (as
1158 defined in Section 8.1) that is thought to be advice-related (due to excess insulin administration) and
1159 occurs more than three times, the overall study will be suspended while the problem is diagnosed. The
1160 study may resume if the underlying problem can be corrected by a protocol or system modification that
1161 will not invalidate the results obtained prior to suspension. The overall study will be stopped in the
1162 event of three serious adverse events related to device malfunction.

1165 **9 MISCELLANEOUS CONSIDERATIONS**

1166 **9.1 Benefits**

1168 One purpose of this research is to reduce the frequency of hypoglycemia and severe hypoglycemic

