1282 The circumstances of all reportable cases of the following will be summarized and tabulated by
1283 treatment group:

1284 • Severe hypoglycemia (as defined in Section 8.1)
1285 • Diabetic ketoacidosis (as defined in Section 8.1)
1286 • Other serious adverse events (SAE) and serious adverse device events (SADE)
1287 • Unanticipated adverse device effects (UADE)

1288
1289 The total number of SH or DKA events per subject will be compared using robust Poisson regression
1290 and the percentage of subjects with at least one event will be compared using Fisher's exact test.

1291
1292 **10.6 Additional Tabulations**
1293 The following tabulations will be performed without statistical testing:

1294 - baseline demographics and clinical characteristics
1295 - flow chart accounting for all subjects for all visits
1296 - visit completion rates for each follow-up visit
1297 - hours of sensor use
1298 - days of sensor use per week
1299 - phone contact completion rates for each follow-up visit
1300 - protocol deviations
1301 - number and reasons for unscheduled visits and phone calls
1302 - device malfunctions requiring study team contact and other reported device issues
1303 - In addition, performance metrics will be tabulated, describing the inControl Advice system and
1304 its components.

1305
1306 **10.7 Interim Analysis**
1307 All CGM-related study endpoints will be analyzed for the first 6 weeks of study intervention in the
1308 first 40 subjects. The purpose of the interim analysis is to support regulatory submissions for the
1309 CGM+DSS system.

1310

1311 **11 DATA COLLECTION AND MONITORING**

1312 **11.1 Case Report Forms and Device Data**

1313 The main study data are collected through a combination of case report forms (CRFs) and electronic
1314 device data files obtained from the study software and individual hardware components. These
1315 electronic device files and electronic CRFs from the study website are considered the primary source
1316 documentation.

1317 **11.2 Document Storage and Retention**

1318 The Investigator of each clinical site will retain all records and documents pertaining to this study.
1319 They will be available for inspection by the appropriate regulatory agencies. In addition, the
1320 Investigator will retain the source documents from which the information entered on the CRFs was
1321 derived. These records are to be retained in a secure storage facility maintained by the investigational

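### Non-DKA severe hyperglycemic events can end device use under 8.6.1 but have no line of their own in the safety endpoints or the Section 10.5 comparison, and non-serious ones reach no planned by-arm safety table

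*Combined protocol and SAP*

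**What the plan says.** Section 8.1 makes severe "hyperglycemia/diabetic ketoacidosis (DKA) as defined below" a reportable adverse event. It then gives two routes to a severe hyperglycemic event. The first is DKA, which has its own criteria for symptoms, ketones, acidosis and treatment in a facility. The second applies "below, or in the absence of DKA if evaluation or treatment was obtained at a health care provider" facility for an acute episode of hyperglycemia with ketosis.

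Both stopping rules refer back to that definition. Section 8.6.1 ends use of inControl Advice (CGM+DSS group) or of the study CGM (CGM group) after "One episode of severe hypoglycemia, or of hyperglycemia/DKA as defined in Section 8.1". The study-level rule in 8.6.2 begins "In the case of inControl Advice resulting in a severe hypoglycemia or severe hyperglycemia event (as" and again points to 8.1. It suspends the study when such events, thought to be advice-related, occur more than three times.

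The analysis sections are narrower. Apart from severe hypoglycemia, the main safety endpoints in 1.3.7 are "Episodes of diabetic ketoacidosis (DKA" and "Other serious adverse events". The by-arm list in 10.5 has severe hypoglycemia, "Diabetic ketoacidosis (as defined in Section 8.1", "Other serious adverse events (SAE) and serious adverse device events (SADE" and unanticipated adverse device effects (UADE). The only formal safety comparison, by robust Poisson regression and Fisher's exact test, is of SH or DKA events.

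**The concern.** The protocol treats a non-DKA severe hyperglycemic event as grave enough to end a subject's device use, yet its safety analysis gives the event no name. Take a subject seen in an emergency department for hyperglycemia with ketosis, with no acidosis and no admission, whom the investigator does not judge to have had a significant medical event. That subject has a reportable adverse event and meets the discontinuation rule, but counts in no safety endpoint and in no row of 10.5.

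This matters because the intervention is insulin-dosing advice, and Section 8.5.5 itself foresees that an under-reading sensor could lead to an unsuitable insulin recommendation. The whole 8.1 class of severe hypoglycemia enters the arm comparison, but only the DKA part of the severe hyperglycemia class does. The SH/DKA comparison could therefore look neutral while subjects in one arm were being taken off the device for severe hyperglycemia.

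**Working it through.** The point concerns which events are covered, so there is no figure in the plan to reproduce. The check follows three kinds of severe hyperglycemic event through the document.

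| Place in the protocol | DKA | Non-DKA, serious under 8.3 | Non-DKA, not serious |
|---|---|---|---|
| 8.1, recorded as a reportable event | yes | yes | yes |
| 8.6.1, ends device use | yes | yes | yes |
| 8.6.2, counts toward suspension if advice-related | yes | yes | yes |
| 1.3.7, main safety endpoint | named | within other serious events | absent |
| 10.5, by-arm tabulation | own line | pooled under SAE/SADE | absent |
| 10.5, Poisson and Fisher comparison | included | not included | not included |
| 10.6, additional tabulations | no named item | no named item | no named item |

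**Can another row of 10.5 catch the last column?**
- The SAE and SADE row requires seriousness. Under 8.3, a facility visit without admission does not meet the hospitalization criterion. The event could still qualify if the investigator judges it a significant medical event, so capture depends on judgment.
- UADE, as defined in 8.3, also covers only serious effects or problems, and only those not already identified. Section 8.5.5 already lists hyperglycemia and ketonemia as risks.
- Section 10.6 has no general adverse event table. Its nearest items are the participant flow chart and the reasons for unscheduled contacts. Neither is an event count, and the section does not ask for tabulation by arm.
- Section 10.3 compares percent time above 300 mg/dL between arms. This is a secondary efficacy measure of sensor glucose and reflects neither ketosis nor facility care.

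**What could a formal test add?** Assume 132 subjects split exactly 2:1, that is 132 × 2/3 = 88 and 132 × 1/3 = 44, with x subjects having an event, all in the CGM+DSS arm. The probability of that table is C(88, x)/C(132, x). The two-sided Fisher p adds every table that is no more probable.

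For x = 4:
- all four in CGM+DSS: (88·87·86·85)/(132·131·130·129) = 0.193
- one in CGM+DSS and three in control: 88·C(44,3)/C(132,4) = 1,165,472/12,082,785 = 0.096
- none in CGM+DSS and four in control: C(44,4)/C(132,4) = 135,751/12,082,785 = 0.011
- sum: p = 0.30

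| Subjects with an event, CGM+DSS vs CGM | Two-sided Fisher p |
|---|---|
| 4 vs 0 | 0.30 |
| 8 vs 0 | 0.0515 |
| 9 vs 0 | 0.029 |

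Nine against none is the smallest such split below 0.05. The suspension rule in 8.6.2 is reached at the fourth advice-related event, well before that.

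**The case against.** The strongest reply is that these events are neither hidden nor ignored. They are recorded, each form is reviewed by the Medical Monitor (8.2), all adverse events go to FDA in the annual IDE report (Table 2), and 8.6.2 can suspend the study. Those that meet 8.3, including by investigator judgment, reach the by-arm SAE row. Section 10.3 compares time above 300 mg/dL and HbA1c between arms. Section 10 calls itself a summary and promises a detailed statistical analysis plan, which is not among the documents.

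Most of this stands, and it rules out several stronger readings that a reader might infer:
- *No safety endpoint or table includes non-DKA events.* Not supported: serious ones fall under other serious adverse events in both 1.3.7 and 10.5.
- *Hypoglycemic harm is counted in full and hyperglycemic harm is not.* Not supported: 8.1 records hypoglycemia only when altered consciousness required another person's active help. Both sides are limited to severe forms. The difference is that one severe class is tabulated whole and the other in part.
- *Most severe hyperglycemic events would be missed.* The documents give no rate for either route.
- *Harm from too little insulin goes wholly uncompared.* Glucose exposure is compared in 10.3; the clinical event is not.

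The reply does not remove the gap. Review by a monitor and annual reporting to a regulator are not comparisons between arms. The list in 10.5 is specific, and a later plan that follows it would carry the omission forward.

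**Conclusion.** The concern holds in a limited form. As a category, non-DKA severe hyperglycemic events are absent from the safety endpoints, the by-arm tabulation and the formal comparison. Serious ones appear only pooled with other serious events. Non-serious ones appear in no planned by-arm safety table, although a single event ends device use.

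The number of events affected cannot be stated from the documents. The conclusion rests on two readings: that 8.6.1 means the whole 8.1 class, which its cross-reference supports, and that 10.5 is a complete list. The reference in 8.6.2 is less tidy, because its parenthesis ties advice-related events to excess insulin, and it is unclear how that applies to hyperglycemia. That passage needs reconciling, but the point stands on 8.6.1 alone.

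The primary efficacy analysis is not affected. The correction should be made before results are known, and its value lies in the descriptive count by arm.

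**What to change.** Keep DKA as its own line in 1.3.7 and 10.5. Add to both a line for severe hyperglycemic events as defined in Section 8.1, in total and split into DKA and non-DKA. In 10.5, tabulate it by treatment group with the number of events and the number and percentage of subjects with at least one. If the total is also tested, label the test supportive and say that it will have little power. Carry the same wording into the detailed statistical analysis plan.

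The cost is a short wording change and one more table row. No new data are needed, because 8.1 already has these events recorded as adverse events, and no clinical rule changes. The small downside is that the reported safety event rate may be slightly higher.
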